### Safety Lab Tests

Chemistry	Hematology	Urinalysis		
Comprehensive Metabolic Panel:	Complete Blood Count:	Urine Dipstick Analysis:		
Light green top (3mL minimum)	Purple top (2mL minimum)	Sterile Urine Container		
Sodium	Hemoglobin	рН		
Potassium	Hematocrit	Color		
Chloride	WBC	Clarity		
Carbon Dioxide	RBC	Specific Gravity		
BUN	MCV	Occult Blood		
Creatinine	MCH	Urobilinogen		
Glucose	MCHC	Ketones		
Calcium	RDW	Protein		
Total Protein	Platelet Count	Glucose		
Albumin	Neutrophils			
ALP	Lymphocytes			
AST	Monocytes			
ALT	Eosinophils			
Total Bilirubin	Basophils			
Lipid Panel:				
Cholesterol	HgbA1c			
LDL cholesterol				
Triglyceride				
Fasting glucose				
Vitamin B12				
Folate				
Pregnancy test				
(bHCG)				
Lactate Gray top (1mL minimum)				

Molecular Biomarkers – In addition to the blood for safety labs, we will collect a minimum of 24.5 mL of blood at each visit for biomarker analysis including FMRP level, MMP9, S6 Kinase, EIF4E, *CYFIP1* mRNA, CYP450 allelic variants, proteomics, mRNA sequencing and metabolome variants. The Edmonton site will collect four EDTA tubes (2mL, 2 x 3mL, and 6mL), one PAXgene tube (2.5mL), and one CPT tubes (8mL). Due to differences in laboratory processing protocols, the Montreal site will collect 4 EDTA tubes (2mL, 3mL, and 2 x 5mL) and one PAXgene tube (2.5mL).

#### **Protein biomarkers**

Plasma, DNA, and peripheral blood mononuclear cells (PBMCs) will be used for the proposed experiments. We consider testing various target proteins including the following.

FMRP level. The level of FMRP has been correlated to the IQ in individuals with Fragile X. Significant variation in FMRP levels can be observed in FXS individuals based on sex, type of tissue examined, degree of FMR1 methylation and presence of mosaicism. FMRP measurements will be performed on lymphocytes, fibroblasts, and epithelial cells (obtained from urine sample) at baseline.

Tissue type: The cells will be obtained from lymphocytes derived from blood, cells from urine, or skin fibroblast. 1) The optional skin biopsy will be carried out after lidocaine or EMLA cream is applied topically and approximately 2 cc of lidocaine is injected so that the procedure is painless. A small punch biopsy is done and then covered with a steristrip and a 4X4 gauze. This will only be done at baseline. However, the aforementioned blood sample and the urine sample (described below) will be obtained at baseline, week 8, and end of treatment/week 16. 2) The urine sample, a non-invasive method, will provide epithelial cell cultures that are alternatives to fibroblast cultures and can also later be derived in stem cells. Methods involve fresh urine samples (< 5h) being centrifuged and the cell pellets being re-suspended and then plated into 24-well tissue culture plates. Urine derived cells are isolated and characterized as previously described (Zhou, T et al. 2011). Numbers of cell clones are counted from each urine sample after they are cultured for 2 weeks. Cell colonies from fresh urine samples often appeared as a cluster of 5–12 cells within 5–7 days. 3) If done with blood, peripheral blood mononuclear cells (PBMC) are used as described later.

Method: FMRP measurements will be done using the Cisbio Human FMRP assay (63ADK038PEC0). The assay uses HTRF (homogeneous time-resolved fluorescence) technology in which fluorescence resonance energy transfer (FRET) occurs between antibody-bound donor and acceptor groups located on the same FMRP molecule via the two fluorophores-conjugated antibodies (Degorce et al., 2009). Operation in a time-resolved fashion eliminates any background fluorescence. The donor is labeled with europium cryptate (Eu³+-Cryptate) and the acceptor is "d2". Total protein concentration is determined using the Thermo Fisher MicroBCA Assay (23235). Protein levels will be determined in triplicate in a 384 well format following the instructions on the assay protocol. Samples are read on the PerkinElmer VictorX5.

Global protein synthesis rate. Fmr1 KO mouse model of FXS show that protein synthesis rates measured *in vivo* are increased in many regions of the brain (Qin et al., 2005). Both genetic manipulation and pharmacological treatment of Fmr1 KO mice with drugs that normalize rates of protein synthesis have been shown to correct some molecular and behavioral phenotypes (Bhattacharya and Klann, 2012; Henderson et al., 2012; Liu et al., 2012; Michalon et al., 2012;

Osterweil et al., 2013). Preliminary data shows that altered protein synthesis can be reliably measured in human fibroblast cultures of patients with Fragile X syndrome and data suggest that it may be correlated to clinical outcomes. Protein synthesis rates will be measured using cell culture and SuNSET assay. During this trial, we aim to measure the critical "molecular phenotype" to understand how it may contribute or co-vary with clinical manifestations and respond to treatment.

We propose to perform Data-independent acquisition mass spectrometry (DIA-MS) analysis on a subset of lymphocytes and fibroblasts to determine the influence of metformin treatment on the cell proteome. DIA-MS is a recently developed MS approach in which all ions within a selected m/z range are fragmented and analyzed in a second stage of tandem mass spectrometry (Doerr et al., 2015). Mass spectra are acquired either by fragmenting all ions that enter the mass spectrometer at a given time (called broadband DIA) or by sequentially isolating and fragmenting ranges of m/z. Metformin is known to alter the translation of numerous proteins, and therefore that part of its molecular response should be gauged by the nature and extent of the proteomic response. The analysis requires approximately 20-40 ug of total protein, which would be obtainable from approximately one-third of blood from a CPT tube. For lymphocytes, the DIA-MS analysis would be performed both before (baseline) and immediately following metformin treatment. For fibroblasts, cells would be subjected to DIA-MS prior to, and following addition of metformin. In this instance, we would be looking for differences in the basic proteomic response to metformin, and whether the nature of this response would correlate with the magnitude of the clinical response.

In addition, we will use mass spectroscopy to study specific metabolites. Indeed, we will establish metabolome variants integrating data from three different platforms into a coherent view on regulation of metabolites in participants. In all three methods ((1) Complex lipids by CSH-QTOF accurate mass / high resolution mass spectrometry, (2) Primary metabolites by the cold injection GC-TOF mass spectrometry, and (3) Exogenous metabolites and biogenic amines by HILIC-QTOF mass spectrometry) we will use 'metabolite targets' for arrays of identified metabolites, with known quantification ions and retention times and specialized internal standards, in addition to detecting 'novel metabolite signals' which may be important to innovate biomarkers and mechanistic understanding of diseases.

Gene expression biomarkers (RNA). Loss of FMRP has been shown to affect gene expression in FMR1KO mice and human. We will therefore obtain RNA from participants at each visit to assess levels of candidate targets.

The loss of FMRP is believed to cause dysregulated translation of its target mRNAs (including MMP9), many of which are critical for synaptic plasticity, maintaining neuronal function, and regulatory control of protein synthesis (Darnell and Klann, 2013). We will perform RNA sequencing on RNA isolated from leukocytes isolated in the blood of participants on either

placebo or metformin at each visit. mRNA sequencing (RNAseq) – As with DIA-MS, RNAseq would be performed before/after treatment of subjects with metformin, and pre- and post-metformin treatment from a subset of participants. mRNA would be purified in the participating laboratories and submitted for RNAseq analysis sequencing/expression core. As with DIA-MS, the mRNA would be isolated from one aliquot of pelleted lymphocytes, either the same pellet used for the DIA-MS experiment or from a portion of the purified RNA.

#### Genomic biomarkers

Molecular measures at the FMR1 locus will include CGG sizing (using a combination of PCR and Southern blot analysis), methylation status, and FMR1 and CYFIP1 mRNA expression using procedures outlined and detailed in our previous studies (Tassone et al., 2000; Tassone et al., 2008; Filipovic-Sadic et al., 2010).

To determine whether the efficiency of response to metformin is dependent on the type of CYP450 allelic variants, we will determine the genotype in DNA samples obtained from lymphocytes of participants and correlate them to the clinical response measures outlined above. Analysis of Cytochrome P450s polymorphisms will be obtained by the xTAGv3 Kits (Luminex Corporation, Austin, TX) on a Luminex 100/200 instrument. Expression levels of targets in the mTOR/p70S6 kinase signaling pathways (Renard et al., 2016) (total and phosphorylated forms) will be measured by western blot analysis, as described in Hoeffer et al. (2012). MMP9 activity will be measured using a Milliplex assay (EMD-Millipore, Billerica, MA) in plasma samples isolated from whole blood collected in EDTA-containing tubes, followed by centrifugation for 10 minutes at 1000 x g within 30 minutes of blood collection. Samples will be diluted 100-fold with assay buffer. Overnight incubation will be carried out for 17 hours at 4°C with shaking. Samples will be measured within one hour of finishing protocol using Luminex bead reader. MMP9 activity will be correlated to clinical improvement measures, as described above.

In addition, several variations in genes involved directly with metformin pharmacokinetics have been identified and will be assessed using next-generation sequencing and Sanger sequencing confirmation. Indeed, transport of metformin into the body is determined by several transporters. We will analyze the sequence for the transporter OCT1 and OCT2 (coded by the genes SLC22A1 and SLC22A2) and Multi-drug and toxic extrusion 1 (MATE1). A recent genomic analysis of response to metformin also identified other candidates including Ataxia telangiectasia mutated (ATM) and other candidate genes who did not reach statistical significance in the study (Zhou, K et al, 2011).

Furthermore, other genes involved in pathways related to FXS, metformin, metabolism or other genes not directly related could also be associated with variation in the response to metformin will be assessed using unbiased exome or genome next-generation sequencing.

Page 27 of 47 1 November 2022 Pro00081059

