## 2) Objectives

- 1. Assess safety and tolerability of metformin in individuals with FXS ages 6 to 35 who are treated over a 4-month period (and an additional 2 years if they participate in the open label extension).
- 2. Assess the benefit of metformin in the treatment of language deficits, behavior problems, and obesity/excessive appetite in individuals with FXS over a 4-month period (and an additional 2 years if they participate in the open label extension).
- 3. Assess the utility of innovative outcome measures, including measures of brain processing (event related potential habituation paradigm and social gaze monitoring using the Tobii Eye Tracker), language/cognitive measures (NIH Toolbox cognitive battery measures and expressive language sampling), a measure of memory (The Memory Game), behavioral and quality of life measures [Aberrant Behavioral Checklist–Community (ABC-C) fragile X version, Child Sleep Habits Questionnaire (CSHQ), Anxiety Depression and Mood Scale (ADAMS) Swanson, Nolan and Pelham questionnaire (SNAP-IV), and Pediatric Quality of Life Questionnaire (PedsQL) Parent Proxy], EuroQol-5D (EQ-5D-3L or EQ-5D-Y), Sensory Profile-2 (up to 15 years old) or Sensory Profile Adolescents/Adults (11 years and older), and Care Related Quality of Life (CarerQoL)], a food questionnaire (Automated Self-Administered 24-Hour Dietary Assessment Tool (ASA24)), in addition to standard measures of outcome [Clinical Global Impression Scale-Severity (CGI-S), Clinical Global Impression Scale-Improvement (CGI-I), Visual Analog Scales (VAS), and Vineland

- Adaptive Behavior Scales-Third Edition (for English speakers) and Second Edition for French speakers)].
- 4. Assess molecular biomarkers that may predict which patients may be likely to benefit from metformin treatment. A panel of molecular biomarkers, including FMRP level, MMP9, S6 Kinase, EIF4E, *CYFIP1* mRNA, CYP450 allelic variants, and metabolome variants, genomic variants, proteomics and mRNA sequencing will be studied.

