mutation (CGG repeats, degree of methylation, and FMRP expression levels), and neurochemical changes in the CNS that can also be measured in blood and fibroblasts (MMP9, S6K, EiF4E, and CYFIP1). Finally, the cytochrome P450 (CYP) isozymes, highly polymorphic drug-metabolizing enzymes, have been demonstrated to be responsible for the metabolism of metformin in humans, mainly via CYP2C11, 2D1, and 3A1/2 (Choi and Lee, 2006). Thus, in this study we will assess if the CYP450 allelic variant genotypes involved in the metformin pharmacokinetics determine the efficiency of response to metformin. Since metformin absorption is done by active transport via the organic cation transport (OCT), we will also assess polymorphism in that gene.

Leveraging the current RCT program and adding an open label extension. New information pointing toward the importance of considering a metformin open-label extension to our current randomized control trial of metformin in individuals with Fragile X syndrome (FXS) has emerged for several reasons. We are therefore adding a 2 year (24 months) optional extension of open-label metformin trial to all participants of our approved RCT of metformin in FXS.

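### The stated biomarker analyses correlate markers with clinical response and do not compare arms, so they cannot separate predictors of metformin benefit from prognostic markers

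*Combined protocol and SAP*

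**What the plan says.** Objective 4 (Section 2) is to "Assess molecular biomarkers that may predict which patients may be likely to benefit from metformin treatment". Section 3 puts the pharmacogenetic part this way: "we will assess if the CYP450 allelic variant genotypes involved in the metformin pharmacokinetics determine the efficiency of response to metformin".

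The matching analyses are in Section 7, Laboratory Evaluations:

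- Genomic biomarkers, CYP450 variants: "we will determine the genotype in DNA samples obtained from lymphocytes of participants and correlate them to the clinical response measures outlined above".
- Genomic biomarkers, MMP9: "MMP9 activity will be correlated to clinical improvement measures, as described above".
- Protein biomarkers, mass-spectrometry proteomics (DIA-MS): "whether the nature of this response would correlate with the magnitude of the clinical response".

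On sampling for the proteome: "For lymphocytes, the DIA-MS analysis would be performed both before (baseline) and immediately following metformin treatment". On RNA: "We will perform RNA sequencing on RNA isolated from leukocytes isolated in the blood of participants on either"; that sentence goes on to name both placebo and metformin, at every visit. The next sentence likens RNA sequencing to DIA-MS and describes it before and after metformin, in a subset.

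Section 8 specifies an ANCOVA for the language outcomes, with the baseline score as covariate and no marker term. It also mentions machine learning and other statistical methods without giving a question or a model. Biomarker blood is scheduled at each visit without restriction by arm (Section 7), and allocation is 1:1 (Section 18).

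**The concern.** A marker predicts benefit from metformin only if the metformin-minus-placebo difference varies with the marker. Clinical change in a treated participant also contains whatever would have happened on placebo. A correlation with change picks up both parts and cannot split them. A marker of milder disease or faster development could then pass for a marker of metformin responders.

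One of the trial's four objectives depends on this distinction. The randomised phase is the only place to make it, because everyone in the open-label extension takes metformin.

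The proteomics raises a second, separate point. The aim for lymphocytes is to learn what metformin does to the proteome. A before-after change in treated participants alone also contains any change over 16 weeks that is not due to the drug.

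**Working it through.** **No figure to reproduce.** The plan gives no sample size, significance level, power or multiplicity rule for Objective 4. The level of 0.016 and the 80% power in Section 8 concern two language measures.

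**Inputs.** From the plan: 60 per group (Section 8) and 1:1 allocation (Section 18). Assumed, because the plan gives no values: correlation r between marker and clinical change, two-sided level 0.05, and marker prevalence q.

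**What each analysis estimates.** Write change = a + b·M + T·(c + d·M), with M the marker and T = 1 for metformin, 0 for placebo. Then b is prognosis and d is prediction.

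- Slope within the metformin arm: b + d.
- Slope over both arms pooled, with 1:1 allocation: b + d/2.
- Marker-by-arm interaction: d.

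Only the interaction isolates d. Section 7 does not say whether its correlations are within arm or pooled, but neither version answers Objective 4.

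**Size for a purely prognostic marker (d = 0).** By Fisher's z, the chance of p < 0.05 is about Φ(atanh(r)·√(n−3) − 1.96). For n = 60, √57 = 7.550:

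- r = 0.2: 0.2027 × 7.550 − 1.96 = −0.43, giving 33%.
- r = 0.3: 0.3095 × 7.550 − 1.96 = 0.38, giving 65%.
- r = 0.4: 0.4236 × 7.550 − 1.96 = 1.24, giving 89%.

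The same formula with n = 120 (both arms pooled, no drug effect) gives 59%, 92% and 99.6%.

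A simulation of 20,000 trials per setting agrees:

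| r | Metformin arm, n = 60 | Metformin arm, n = 30 | Interaction, 60 per arm |
|---|---|---|---|
| 0 | 5% | 5% | 5% |
| 0.2 | 34% | 18% | 5% |
| 0.3 | 66% | 37% | 5% |
| 0.4 | 90% | 60% | 5% |

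The n = 30 column shows how the figures fall in a smaller subset. DIA-MS is planned only in a subset, whose size is not given.

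**Power of the interaction test.** For a binary marker with outcome SD 1 and n per arm, SE = √[(2/n)(1/q + 1/(1−q))], and 80% power needs a difference of (1.96 + 0.84)·SE between the treatment effects in marker-positive and marker-negative participants. At n = 60:

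- q = 0.5: SE 0.365, difference 1.02 SD.
- q = 0.3: SE 0.398, difference 1.12 SD.
- q = 0.1: SE 0.609, difference 1.70 SD.

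For scale, the plan's expressive-language effect is (20.7 − 13.6)/8.4 = 0.845 SD. If all of it were confined to marker-positive participants, interaction power would be 64%, 56% and 28% at these three prevalences. These figures are for one marker with no multiplicity adjustment.

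**The case against.** The strongest defence is that the text is under-specified rather than wrong. The objective is worded cautiously, and correlating a marker with response does not rule out doing so by arm. For CYP450 and transporter genotypes, chosen for their role in metformin pharmacokinetics, the documents give no reason to expect any relation with change on placebo. At r = 0 the correlation errs no more often than the interaction test. This limits the size of the problem for those genotypes. It does not make the stated analysis a test of prediction, and it does not cover MMP9 or the wider panel.

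Several stronger readings are tempting and do not hold:

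- *The placebo group goes unused for Objective 4.* The RNA-sequencing sentence includes placebo participants, and blood is drawn in both arms. The gap lies in the stated analyses, and in the proteomic sampling as described.
- *The fibroblast experiment also lacks a placebo control.* There metformin is added to cells in culture and the untreated cells are the control, so change over 16 weeks does not apply. The sentence on correlating with clinical response directly follows that experiment and probably refers to it. That correlation still cannot separate prognosis from prediction.
- *FMRP must track language gain regardless of treatment.* The protocol says "The level of FMRP has been correlated to the IQ in individuals with Fragile X". That concerns IQ level, not change over 16 weeks.
- *Practice effects will drive the correlations.* Section 7 describes practice effects on the primary measure as negligible.
- *Prognostic markers will be reported as predictors.* The plan does not say how results will be reported. It supports only that the two cannot be distinguished.

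It is also fair to object that interaction tests here have modest power. That is a reason to call them exploratory, not to replace them with a test of a different question.

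**Conclusion.** The concern holds in limited form. As stated, the marker-outcome analyses cannot answer Objective 4, because none compares arms. The rates of 33%, 65% and 89% against about 5% rest on the assumed correlations of 0.2 to 0.4, on 60 participants per arm with marker data, and on an unadjusted 0.05 level. They show how far the two tests can diverge and do not forecast the result for any named marker.

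The lymphocyte proteomics has a separate gap, since no placebo comparison is described, and the two RNA-sequencing sentences need reconciling. The primary endpoint is unaffected. The change should be made before the assays are run.

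**What to change.** 1. **Test of prediction.** Under Genomic biomarkers, and for the correlation with clinical response under Protein biomarkers, state that prediction is tested by the interaction of the baseline (Visit 1) marker with treatment arm, in all randomised participants with marker data. Show the marker-outcome relation for each arm side by side, and call correlations within the metformin arm descriptive.
2. **Status.** Label these analyses exploratory. Prespecify a short marker list with multiplicity control; the 5% error rate is per marker, and the panel extends to exome or genome sequencing.
3. **Assay subsets.** State that the lymphocyte DIA-MS and RNA-sequencing subsets are drawn from both randomised arms, and compare Visit 1 to Visit 3 change between arms. The DIA-MS text names the CPT tube as the protein source, and only the Edmonton collection list includes one, so say which sites contribute.
4. **No change** is needed to the fibroblast before-after comparison in culture.

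The cost is mainly protocol wording, since blood from both arms is already scheduled. The real price is that part of a fixed assay budget goes to placebo samples. With the power shown above, only large differences between marker subgroups are likely to be detected.

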### **Gut Microbiome**

Stool collected from participants will be stored in the biobank and used by researchers in the future to, for example, look at the differences in the gut microbiome before and after treatment. The OMNIgene GUT OMR-200 stool collection kit will be utilized by the participant (with assistance from the caregiver if needed) to collect a sample at visits 1 and 3 (and the extensions visits after 1 and 2 years) and once from controls. The kit allows for transport and storage at room temperature for 60 days.

#### Other, Non-Outcome Measure Procedures:

Demographics – Basic demographic information will be collected on all study subjects at the screening/baseline visit. This information includes, but is not limited to, date of birth, race, ethnicity, socioeconomic status, education of parents, parental occupation, and parental salary range.

Medical Examination – This will be carried out by the Co-PI and the nursing team at each site and may include growth percentiles, vitals, a detailed medical history, general physical and neurological examination, and review of medical records (paper, electronic), laboratory testing, and educational record, as applicable. In addition, a detailed family history may be obtained if medically necessary. A medical history and exam will be conducted at the screening/baseline visit. A medical exam and a review of recent history will take place at each subsequent visit.

The complete schedule of all study procedures is also listed in a table format below:

	Main Study			Open-label Extension		
Assessment	Visit 1 Week 1, Day 0	Visit 2 Week 8 ±7 days	Visit 3 Week 16 ± 7 days	Visit 1* Week 1	Visit 2 Week 52 ±7 days	Visit 3 Week 104 ±7 days
Informed Consent	X			X**		
Inclusion/Exclusion Criteria***	X					
Medical History	X				X	X
Physical and Neurological Exam	X	X	X	X	X	X
Vital Signs	X	X	X	X	X	X
Adverse Events a	X	X	X	X	X	X
Concomitant Medications a	X	X	X	X	X	X
Autism Diagnostic Observation Schedule (ADOS-2)	X					
Leiter-III	X				X	X
Clinical Global Impression Scale – Severity (CGI-S)	X					
Clinical Global Impression Scale – Improvement (CGI-I)		X	X	X	X	X
Anxiety Depression and Mood Scale (ADAMS)	X	X	X	X	X	X
Expressive Language Sampling (ELS)	X		X	X	X	X
Eye Tracking Measures b	X		X	X	X	X
Event Related Potential (ERP) Measures b	X		X	X	X	X
NIH Toolbox Cognitive Battery Measures b	X		X	X	X	X
Visual Analogue Scale (VAS)	X	X	X	X	X	X
Vineland Adaptive Behavior Scales—Third Edition (VABS-III)	X		X	X	X	X
Aberrant Behavior Checklist–Community (ABC-C)	X	X	X	X	X	X

Child Sleep Habits Questionnaire (CSHQ)	X	X	X	X	X	X
Swanson, Nolan and Pelham Questionnaire (SNAP-IV)	X	X	X	X	X	X
Pediatric Quality of Life (PedsQL) Parent Proxy Questionnaire	X	X	X	X	X	X
EuroQol-5D (EQ-5D)	X	X	X	X	X	X
Care Related Quality of Life (CarerQoL)	X	X	X	X	X	X
Sensory Profile-2/Sensory Profile Adolescents/Adults	X	X	X	X	X	X
Automated Self- Administered 24-Hour Dietary Assessment Tool (ASA24)	X		X	X	X	X
The Memory Game (online) b	X		X	X	X	X
Blood Draw	X	X	X	X	X	X
Urine Collection	X	X	X	X	X	X
Stool Collection	X		X	X	X	X
Skin Biopsy (optional)	X					
Dispense Study Drug	X	X			X	
Collect Study Drug		X	X		X	X

- a: Also assessed at phone calls at Weeks 1, 2, 3, 4, and 12 and during the optional open label extension at weeks 1, 2, 3, 4, 20, 36, 52, 68, 84, 100
- b: If subject is capable of completing assessment
- \* If a participant begins the extension study within 1 year of ending the RCT portion of the study, Visit 3 of the RCT will be considered to be Visit 1 of the extension and the participant would be seen at a 1 year follow up from when they had their Visit 3 of the RCT portion. So assessments, safety laboratory and biological sample collections (blood, urine, stool) will not be duplicated if no change in medical condition has occured.
- \*\* Informed consent for the open label extension will be done at Visit 3 of the RCT portion if possible, otherwise if a participant in the RCT portion decides to participate in the open label extension later, consent will be done then.
- \*\*\* Inclusion criteria, which are met at the beginning of the RCT, will be used to participate in the open label extension as well. If a participant is over 35 by the start of the extension or any time during the extension they will still be included.

